## ● Statistics

- Descriptive statistics to calculate the prevalence and impact of musculoskeletal symptoms
- Descriptive statistics to characterize demographic information on participants
- Linear mixed models: Used to test for an association between pain and the targeted micro-break intervention
- Statistical significance is set at 0.05 (Bonferroni adjustment for measurement on 11 body parts.)

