### ● Recruitment Methods

- An E-mail will be sent out to attending physicians and residents affiliated at GWU and Children's National inviting them to participate in the study.

- **Research Locations**

- George Washington University Hospital
- Children's National Medical Center

[figure not shown]
- **Methods**

- **Intervention**

- **Otolaryngology stretching micro-breaks (OSMB)**= standardized microbreak stretch that is designed to perform intraoperatively within the sterile field at medically convenient 20-40 min intervals throughout each procedure.

- **Assessment tools (see the table of content to view survey)**

[figure not shown]
- Preliminary questionnaire- given at the beginning of the study
    - Assess demographic information, ergonomic questions, and musculoskeletal symptom questions
  - Pre-surgery questionnaire (baseline)- given prior to each surgery to establish a baseline
    - Body part discomfort (validated survey with 0-5 score on the neck, shoulder R/L, hand R/L, lower/upper back, knee R/L, foot R/L)

- Post-surgery questionnaire for CONTROL day- given after each surgery
  - Surg-TLX and GOAL questionnaire- assess the degree of difficulty of the surgery
  - Body part discomfort sore
- Post-surgery questionnaire for INTERVENTION day- - given after each surgery
  - Surg-TLX and GOAL questionnaire- assess the degree of difficulty of the surgery
  - Body part discomfort sore
  - Questions on OSMB
- Exit questionnaire after the study is completed
  - 2 questions asking whether the participant would incorporate OSMB in their routine OR cases, and would recommend OSMB to colleagues.

- **Study design**

- Crossover study design
- Control: 3 Non-OSMB surgical days
- Intervention: 3 OSMB surgical days
- In order to reduce confounding variables, study will focus on open neck cases. (e.g. thyroidectomy, parathyroidectomy, neck dissection, etc)
- We will adjust for surgical duration, and use Surg-TLX, and GOAL questionnaires to show no statistically significant difference between control and intervention surgical cases.
- Outcome measures
  - Primary outcome= difference between self-reported body part discomfort score from before/after surgery
    - Control the surgical environment and difficulty using Surg-TLX and GOAL questionnaires. The score should be statistically insignificant among various surgeries.
  - Secondary outcome= impact of OSMB on physical performance, discomfort/pain, fatigue, and mental focus

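### Bonferroni over the 11 body parts is valid, but Holm step-down on the same p-values is never worse for deciding which parts benefit

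*Protocol*

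**What the plan says.** The Statistics section of the protocol sets the error level and the multiplicity method together: "Statistical significance is set at 0.05 (Bonferroni adjustment for measurement on 11 body parts". The p-values come from the models named in the same section: "Linear mixed models: Used to test for an association between pain and the targeted micro-break intervention".

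The parts are listed under Assessment tools in Methods: "neck, shoulder R/L, hand R/L, lower/upper back, knee R/L, foot R/L". The pre-surgery and both post-surgery questionnaires show the same 11 items.

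Under Outcome measures the protocol gives "Primary outcome= difference between self-reported body part discomfort score from before/after surgery". It names no single body part or composite as primary and no rule for declaring success. The Sample size section gives 26 participants by site and grade (9 + 8 + 9), without a power calculation.

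**The concern.** The protocol itself fixes the adjustment method, so this is not a detail left to a separate analysis plan. Bonferroni controls family-wise error, and nothing is wrong with its validity. The question is whether it is the best choice when 11 separate verdicts are to be given.

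Holm applies rising thresholds to the ordered p-values, and none of them is below the Bonferroni level. Every part declared significant by Bonferroni is therefore also declared significant by Holm, under the same error guarantee and with no added assumption. What is at stake is power for the second and later parts. That matters somewhat more here because the sample is a count of named staff groups at two sites and looks hard to enlarge.

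**Working it through.** **Inputs from the protocol.** Family-wise level 0.05 and Bonferroni over 11 parts (Statistics); the list of parts (Assessment tools); 26 participants (Sample size); a crossover with 3 control and 3 intervention days (Study design).

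**Assumed, because the protocol gives no values.** Standardised effect 0.3 to 0.8 SD of the within-person difference; correlation between parts 0 to 0.8; 1 to 11 parts truly affected; 26 or 20 complete participants.

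**Step 1: the plan's own level.** Neck 1 + shoulders 2 + hands 2 + lower and upper back 2 + knees 2 + feet 2 = 11, which agrees with the stated number. The level per part is 0.05/11 = 0.004545. The family-wise error is at most 11 × 0.004545 = 0.05. If the tests were independent it would be 1 − (1 − 0.004545)^11 = 0.0489, against 1 − 0.95^11 = 0.431 with no adjustment. The plan's method does what it says.

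**Step 2: Holm thresholds.** For the i-th smallest p-value the threshold is 0.05/(12 − i), and testing stops at the first failure:

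0.00455, 0.00500, 0.00556, 0.00625, 0.00714, 0.00833, 0.0100, 0.0125, 0.0167, 0.0250, 0.0500.

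The smallest of these equals the Bonferroni level. Two things follow. Holm rejects everything Bonferroni rejects. Holm makes a first rejection exactly when Bonferroni does.

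**Step 3: size of the gain.** Each participant contributes one mean difference, intervention minus control, tested by a two-sided paired t. With complete, balanced 3 + 3 days and no covariates, this is the same test as a mixed model with participant and participant-by-condition effects.

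Bonferroni power has a closed form. With n = 26 and 0.6 SD the noncentrality is 0.6 × √26 = 3.059, on 25 degrees of freedom with two-sided critical value 3.1175, and the power is 0.491. Holm needs simulation. With 20,000 trials per scenario, 0.6 SD and correlation 0.5:

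| Parts affected | Bonferroni, average power per affected part | Holm | Gain (points) |
|---|---|---|---|
| 1 | 0.496 | 0.496 | 0.0 |
| 2 | 0.492 | 0.499 | 0.7 |
| 3 | 0.490 | 0.505 | 1.5 |
| 4 | 0.491 | 0.514 | 2.3 |
| 7 | 0.496 | 0.550 | 5.4 |
| 11 | 0.491 | 0.622 | 13.1 |

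The simulated Bonferroni column lies within 0.005 of the closed form. Repeating selected scenarios with fresh random numbers moved entries by at most 0.006.

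- Expected number of affected parts found: 1.96 vs 2.06 of 4; 3.47 vs 3.85 of 7.
- Chance of finding at least one affected part, the same for both methods: 0.808 (4 affected), 0.884 (7), 0.926 (11).

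**Step 4: sensitivity (Bonferroni vs Holm).**

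| Scenario (correlation 0.5) | 4 affected | 7 affected | 11 affected |
|---|---|---|---|
| 0.3 SD, n = 26 | 0.079 vs 0.082 | not tabulated | 0.077 vs 0.093 |
| 0.8 SD, n = 26 | 0.818 vs 0.841 | 0.818 vs 0.869 | 0.819 vs 0.925 |
| 0.6 SD, n = 20 | 0.330 vs 0.347 | 0.333 vs 0.373 | 0.330 vs 0.428 |

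With 7 affected at 0.6 SD and n = 26, Holm gives 0.547, 0.550 and 0.543 at correlations 0, 0.5 and 0.8, against about 0.49 for Bonferroni. Correlation is not what drives the gain there.

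**Step 5: error control.** With no part affected, simulated family-wise error was the same for both methods: 0.0505 at correlation 0 (simulation error about 0.0015), 0.039 at 0.5 and 0.022 at 0.8. With some parts affected, Holm's error on the unaffected parts was at most 0.0485. In no simulated trial did Bonferroni reject a part that Holm did not.

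**Step 6: cost in intervals.** If Bonferroni intervals are kept beside Holm tests, a part can be significant while its interval includes zero. At 0.6 SD and correlation 0.5, at least one such part occurs in 0.5% of trials with 1 affected part, 10% with 4, 30% with 7 and 60% with 11.

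**The case against.** The strongest reply is that a valid, pre-specified adjustment with the right count is not a defect, and that the same remark could be made of any trial using Bonferroni. That stands as far as validity goes and is why the point ranks as optional. It does not remove the point: the document fixes a method for which a replacement exists that is never worse for the decisions it makes.

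Second, the dominance covers significance decisions only. Bonferroni has simple simultaneous intervals that always agree with its tests, and the mismatch under Holm is commonest where its power gain is largest. This stands and must be disclosed with the change.

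Third, the gain is nil to about 2 points with 1 to 4 affected parts. With 4 affected it is a tenth of a body part (2.06 − 1.96 = 0.10). The 13-point figure needs all 11 parts, including hands, knees and feet, to improve equally, which nothing in the protocol supports. This stands too, and so does the remark that the benefit depends on an aim the protocol does not state. If success means any one part, Holm changes nothing.

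Last, the power figures rest on assumed effects and a normal paired t. They leave out the planned adjustment for surgical duration, missing days and the coarse five-level scale with a possible floor. The figures are therefore illustrative. The dominance is not affected, because Holm uses only the 11 p-values.

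**Conclusion.** The point holds as an optional, low-cost improvement. The stated Bonferroni rule is correct and controls error at 0.05. Holm gives the same guarantee and never declares fewer parts, whatever the effects, correlation or model.

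The practical gain is nothing for a first significant part. Under the assumed 0.6 SD, correlation 0.5 and 26 complete participants, it is nil to about 2 points of average power with up to 4 affected parts and about 5 with 7. About 13 points is an upper extreme that requires all 11 parts to improve equally. Confidence is high in the dominance; the sizes depend on the assumptions above.

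**What to change.** Replace the significance sentence in the Statistics section with:

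> Family-wise two-sided alpha is 0.05 across the 11 body-part treatment effects, controlled with the Holm step-down procedure; Holm-adjusted p-values are reported.

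If Bonferroni simultaneous intervals are also reported, add that they are not matched to the Holm tests, so that a part may be significant while its interval includes zero.

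The cost is one or two sentences, with no new data, no change to the mixed models and no loss of family-wise error control. The one real downside is that intervals matching Holm are less simple. The change should be made before the data are analysed, since a later switch could look driven by the results.

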## Preliminary Questionnaire

Confidential

Ergonomic survey  
Page 1 of 4

### Preliminary questionnaire

Record ID

---

#### Demographic information

Today's date

---

What is your gender?

- Male
- Female
- Transgender
- Other
- Prefer not to answer

Other (please specify)

---

What is your age?

---

What is your height in inches?

---

What is your weight in pounds?

---

BMI

---

What is your dominant hand?

- Left
- Right
- Both

What is your surgical title?

- Resident
- Fellow
- Attending

What is your postgraduate year (PGY) equivalent level?

- PGY1
- PGY2
- PGY3
- PGY4
- PGY5

How many years of surgical training and/or practice have you completed?

- 0-1 year
- 2-5 years
- 6-10 years
- 11-20 years
- Over 20 years

How many days a week do you perform surgery?

---

How many cases do you perform on a surgery day?

---

Confidential

Page 2 of 4

What is the average duration of each case in hours?

Do you have an exercise routine?

Yes  
 No

How many days a week do you exercise?

What form of exercise(s) do you perform? (select all that applies)

Stretching  
 Yoga  
 Pilates  
 Strength training  
 Cardio training (running, walking, swimming, cycling, etc.)  
 Other

Other (please specify)

**Ergonomic Questions**

Have you experienced any work-related musculoskeletal symptoms while performing the surgery?

Yes  
 No

What is the PRIMARY area of your body that is most bothersome to you? (select one answer)

Neck  
 Shoulder  
 Lower back  
 Upper back  
 Hips  
 Legs  
 Feet  
 Arms  
 Hands  
 None

What is the SECONDARY area of your body that is most bothersome to you? (select one answer)

Neck  
 Shoulder  
 Lower back  
 Upper back  
 Hips  
 Legs  
 Feet  
 Arms  
 Hands  
 None

What is the TERTIARY area of your body that is most bothersome to you? (select one answer)

Neck  
 Shoulder  
 Lower back  
 Upper back  
 Hips  
 Legs  
 Feet  
 Arms  
 Hands  
 None

Confidential

Page 3 of 4

---

When did you begin to experience these musculoskeletal symptoms?

PGY1  
 PGY2  
 PGY3  
 PGY4  
 PGY5  
 During fellowship  
 0-1 year into practice  
 2-5 years into practice  
 6-10 years into practice  
 11 or more years into practice

---

How often do these musculoskeletal symptoms occur?

Rarely  
 Half of surgery cases  
 Most surgery cases  
 Every surgery case

---

Please estimate the timeframe of symptom onset?

< 30min  
 30min to 1hr  
 1-3hrs  
 3-6hrs  
 >6hrs  
 Post-surgery  
 Following day  
 Other

---

Other (please specify)

---

Does the use of specific surgical equipment elicit symptoms more frequently? (select all that applies)

Headlight  
 Robot  
 Endoscopic instruments  
 Loupes  
 Microscope  
 Other

---

What risk reduction strategies do you perform in the OR to help alleviate musculoskeletal issues? (select all that applies)

Ignore it  
 Adjust the surgical field  
 Change the bed height  
 Use a step stool to adjust the height  
 Change instruments  
 Stools  
 Standing pads  
 Timed-Breaks  
 Intraoperative stretching  
 Change position  
 Time away from the OR  
 Treatment  
 Other

---

Others (please specify)

---

Have you had to stop performing this type of surgery due to musculoskeletal symptoms?

Yes  
 No

---

Have you ever taken time off of work due to musculoskeletal pain/injury?

Yes  
 No

---

*Confidential*

Page 4 of 4

---

Have you ever seen any of the following for treatment or consultation? (Select all that apply)

- No treatment
- Massage therapist
- Acupuncture
- Personal trainer
- Physical therapist
- Chiropractor
- PM&R
- Physician
- Surgeon
- Other

---

Other (please specify)

---

Do you routinely stretch or exercise specific muscle groups outside of the operating room to improve trouble areas?

- Yes
- No

---

Have you had any formal training, lectures, or discussion regarding the following areas? Check all that apply

- Posture/body mechanics in the OR head position, shoulders, spine, pelvis
- Ergonomic set up of operating table, microscope, robot
- Patient transfer techniques
- Others
- None

---

Others (please specify)

---

Are you concerned that your pain would limit the ability to perform surgery in the future?

- Yes
- No

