### ● Purpose of the study

- To gather baseline data on the prevalence and impact of musculoskeletal symptoms among otolaryngologists in George Washington University Hospital network.
- To examine the influence of otolaryngology stretching micro-breaks (OSMB) on their physical performance, mental focus, and self-reported pain and discomfort among otolaryngologists in George Washington University Hospital network.

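### The symptom-frequency item in the preliminary questionnaire has no answer between rarely and half of cases, so surgeons with symptoms in a substantial minority of cases must answer too low or too high

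*Protocol*

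**What the plan says.** The first aim under Purpose of the study is "To gather baseline data on the prevalence and impact of musculoskeletal symptoms among otolaryngologists" in the hospital network. The Statistics section plans "Descriptive statistics to calculate the prevalence and impact of musculoskeletal symptoms". The data come from the preliminary questionnaire, given once at the start of the study.

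In that form, the Ergonomic Questions open with a Yes/No screening item: "Have you experienced any work-related musculoskeletal symptoms while performing the surgery". Items on the most bothersome body areas follow, and then three follow-up items:

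- Career onset, "When did you begin to experience these musculoskeletal symptoms": ten options from PGY1 to 11 or more years into practice.
- Frequency, "How often do these musculoskeletal symptoms occur": four options, namely rarely, "Half of surgery cases", most cases and every case.
- Within-case onset, "Please estimate the timeframe of symptom onset": eight options, the last being Other with a free-text field.

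The frequency item has no Other option and no free text. No definition of rarely is printed.

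**The concern.** How often symptoms occur is one of the main ways this form describes their impact, and the distribution over the printed categories is itself the result to be reported. Three of the four answers are shares of cases (half, most, all). The fourth is an undefined adverb. The range from occasional symptoms up to just under half of cases has no category of its own.

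A surgeon in that range has to pick a neighbour. Choosing rarely understates the burden; choosing half overstates it. Two surgeons with the same experience may choose differently, so the direction of the error is unknown. A separate statistical analysis plan could not repair this, because the loss occurs when the answer is given.

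**Working it through.** The protocol states no target figure for this item, so there is nothing to reproduce. The check compares the answer options and then sets the scale of one misplaced answer.

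**Options, in order of frequency**

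| True share of cases with symptoms | Fitting answer on the form |
|---|---|
| Very few | Rarely |
| A substantial minority, e.g. a quarter to a third | None |
| About half | Half |
| More than half, not all | Most |
| All | Every |

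The within-case onset item, printed directly below, does have Other with free text. The frequency item has no such outlet.

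**Scale of one misplaced answer**

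Input: planned N from the Sample size section, 9 + 8 + 9 = 26.

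- All 26 as denominator: 1/26 = 0.038, or 3.8 percentage points. This is the minimum.
- Symptomatic surgeons only: the number is not given. If it were 20 (assumed), 1/20 = 0.05, or 5.0 points.

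**Scale of several**

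Let k be the number of surgeons in the gap and n the denominator. If all k choose the same neighbour, that category is inflated by k/n. The protocol gives no basis for k, so the values below are assumptions that show the range.

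| k (assumed) | n = 26 | n = 20 (assumed) |
|---|---|---|
| 1 | 3.8 points | 5.0 points |
| 3 | 3/26 = 11.5 points | 3/20 = 15.0 points |
| 5 | 5/26 = 19.2 points | 5/20 = 25.0 points |

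If the k surgeons split between the two neighbours, the same total error is shared between rarely and half. The reported share with symptoms in at least half of cases is then too high by the number who rounded up, divided by n. That number cannot be identified from the data.

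**What does not depend on this item**

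- Prevalence: taken from the Yes/No screening item.
- Primary outcome: the before/after difference in body part discomfort score, collected on the pre- and post-surgery forms.
- Linear mixed model: tests the association of pain with the micro-break intervention.
- Other descriptors of impact on the same form, such as time off work, having had to stop this type of surgery and treatment sought, each have their own item.

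**The case against.** The strongest reply is that this is simply a coarse ordinal scale in a descriptive survey. Respondents will round to the nearest answer, and nobody can say how many of the 26 are affected. All of that is true, and it limits the weight of the point. It does not remove the gap: an ordinal scale may be coarse, but it should cover the range, and here a plausible range has no category.

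A reader might infer three stronger things, which the protocol does not support.

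- *Surgeons without symptoms have no place on the form.* The screening item already records them, and the follow-up items refer back to these symptoms, meaning those just asked about. The body-area items do offer None, even for "What is the PRIMARY area of your body that is most bothersome to you? (select one answer". But the same list is reused for the second and third areas, where a surgeon with one sore area needs None, so it is weak evidence that symptom-free surgeons are meant to read on. No skip instruction is printed, but other plainly conditional items, such as exercise days per week, are also printed without one, and an electronic form may branch without this showing in print. Nothing says an answer is compulsory. What stands is only that the denominator for the follow-up items is worth stating.
- *Onset before PGY1 is misattributed to training.* The screening item limits the symptoms to work-related ones during surgery, so earlier onset is largely out of scope.
- *The baseline figures as a whole are wrong.* Prevalence, body area and within-case onset each have suitable answers. Only the frequency distribution has the gap.

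**Conclusion.** The point holds for one item. The frequency scale leaves out the range between rarely and half of cases, and the resulting error cannot be corrected in analysis. Each misplaced answer shifts a category by at least 3.8 percentage points, taking all 26 planned participants as respondents; a smaller number of respondents or a symptomatic-only denominator makes the shift larger. The total distortion is unknown because the protocol gives no information on how many surgeons fall in the gap.

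The consequence is minor. It touches one descriptive table under the first purpose and leaves prevalence, the primary outcome and the mixed model untouched. It is worth making because the change is specific and nearly free.

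**What to change.** 1. Add one answer to the frequency item between rarely and half, for example 'Some surgery cases (fewer than half)'.
2. State that the frequency and career-onset items are reported among surgeons who answered Yes to the screening item, with that number given as the denominator.

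The cost is one answer option on a form given once and one sentence on reporting. No other item and no part of the primary analysis changes. If some surgeons have already completed the form, ask them this one item again, or tabulate their answers separately from those given on the revised scale.

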### ● Sample size

- N= 26
  - 9 attending physicians and 8 residents at GWU
  - 9 attending physicians at Children's National Medical Center

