**Body part discomfort scores:**

- 1 Not uncomfortable**
- 2 Barely uncomfortable**
- 3 Quite uncomfortable**
- 4 Very uncomfortable**
- 5 Extremely uncomfortable**

|                 | 1                     | 2                     | 3                     | 4                     | 5                     |
|-----------------|-----------------------|-----------------------|-----------------------|-----------------------|-----------------------|
| Neck            |  |
| Shoulder, right |  |
| Shoulder, left  |  |
| Hand, right     |  |
| Hand, left      |  |
| Lower back      |  |
| Upper back      |  |
| Knee, right     |  |
| Knee, left      |  |
| Foot, right     |  |
| Foot, left      |  |

What was your primary position during the surgery?

- Standing
- Seated
- Standing and Seated

What surgical equipments have you used during the case? (select all that applies)

- Headlight
- Robot
- Laparoscopic equipment
- Loupes
- Microscope
- Other

Other (please specify)

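### The baseline equipment item cannot separate surgeons who do not use a device from those who use it without more frequent symptoms

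*Protocol*

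**What the plan says.** The first aim in the Protocol, Purpose of the study, is "To gather baseline data on the prevalence and impact of musculoskeletal symptoms among otolaryngologists" in the hospital network. The Statistics section plans "Descriptive statistics to calculate the prevalence and impact of musculoskeletal symptoms" for it. The data come from the preliminary questionnaire.

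Under Ergonomic Questions that form asks "Does the use of specific surgical equipment elicit symptoms more frequently? (select all that applies". The boxes are headlight, robot, endoscopic instruments, loupes, microscope and other. The only other preliminary item that names devices concerns training, with the option "Ergonomic set up of operating table, microscope, robot". It says nothing about use.

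Both post-surgery forms (control and intervention) ask "What surgical equipments have you used during the case? (select all that applies". Their list is headlight, robot, laparoscopic equipment, loupes, microscope and other. The Study design text says that the "study will focus on open neck cases".

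**The concern.** The answer depends on exposure: a surgeon who never uses a robot cannot say whether it brings on symptoms more often, and leaves the box blank. So does a surgeon who uses the robot without trouble, and so does one who skips the question. Other items on the same form avoid part of this. The body-area and training items offer a none option, and the treatment item offers a no-treatment option.

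At stake is the baseline picture of equipment. If a device has few users, a high symptom rate among them appears as a small percentage of the group. If use differs widely between devices, the order of the percentages need not be the order of the symptom rates among users. The wording of the form is fixed in the protocol, and no analysis plan can recover a denominator that was never collected.

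**Working it through.** **1. Is use recorded anywhere?**

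| Source | What it records | Does it give habitual use by device? |
|---|---|---|
| Preliminary form, demographic items | Operating days, cases per day, case length, exercise | No |
| Preliminary form, equipment item | Devices that elicit symptoms more often | No |
| Preliminary form, training item | Training in set-up | No |
| Post-surgery forms, equipment item | Devices used in one study case | No: study cases only, with a focus on open neck surgery |

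The post-surgery lists also have laparoscopic equipment where the preliminary list has endoscopic instruments, so that row cannot be matched between forms.

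**2. What a percentage from this item measures.** For each device,

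P(ticked) = P(uses it) × P(symptoms more frequent | uses it).

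Only the left side is observed. Restricting to respondents who report work-related symptoms conditions both factors on having symptoms and leaves the product in place.

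**3. Sample size.** The Sample size section gives "9 attending physicians and 8 residents at GWU" and 9 attending physicians at the second site: 9 + 8 + 9 = 26, as stated. The protocol gives no figure for device use or for symptom rates by device, so there is no plan figure to reproduce. All rates below are assumptions.

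**4. What use alone can do.** Hold the rate among users at 50% for every device:

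- 5 users: 0.5 × 5 / 26 = 9.6%
- 10 users: 0.5 × 10 / 26 = 19.2%
- 20 users: 0.5 × 20 / 26 = 38.5%

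This is a fourfold spread between devices with the same true rate. Because the rate is held equal by construction, it shows what is possible and not what is likely.

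**5. Can the order reverse?** Let 30% of users of device A and 70% of users of device B have more frequent symptoms.

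| Use of A | Use of B | A over all respondents | B over all respondents | Order |
|---|---|---|---|---|
| 90% | 20% | 0.9 × 0.3 = 27% (7.0 of 26) | 0.2 × 0.7 = 14% (3.6 of 26) | Reversed |
| 90% | 60% | 27% (7.0 of 26) | 0.6 × 0.7 = 42% (10.9 of 26) | Correct |
| 100% | 100% | 30% (7.8 of 26) | 70% (18.2 of 26) | Correct |

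Reversal needs the ratio of use, A to B, to exceed 0.7 / 0.3 = 2.33. With A at 90%, B's use must be below 0.9 / 2.33 = 39%.

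**6. Does use or symptom rate dominate?** Five devices were simulated, with use and symptom rate drawn uniformly and independently from assumed ranges, 4,000 draws per row. The last two columns give the mean rank correlation of the all-respondent percentage with each factor.

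| Use range | Symptom rate among users | With use | With symptom rate |
|---|---|---|---|
| 10–100% | 40–60% | 0.91 | 0.18 |
| 10–100% | 20–60% | 0.76 | 0.41 |
| 10–100% | 5–80% | 0.55 | 0.62 |
| 70–100% | 5–80% | 0.15 | 0.93 |
| 80–100% | 20–60% | 0.17 | 0.92 |

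Use dominates when it varies widely between devices and symptom rates vary less. When most surgeons use every device, the distortion is small.

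**The case against.** The best defence is that the protocol plans neither a ranking of devices nor a rate per device. Its aim is prevalence and impact in this group, and for that the share of all surgeons who attribute symptoms to a device is a legitimate measure of burden: a device that troubles 3 of 26 is a smaller group problem than one that troubles 10. This stands, and it is why the share of all respondents should stay in the report. It does not make a blank box interpretable.

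The item also asks for a comparison within each surgeon, whether symptoms come more frequently with a device. That weakens a reading in which ticks merely count users, and any redesign should keep it. A non-user still cannot make the comparison and still leaves a blank.

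Numbers among users will be small. For a device with 5 users of whom 3 tick, the exact 95% interval is roughly 15% to 95%. A ranking by user-based rates would be mostly noise for rare devices. This stands as a limit on what the fix can deliver.

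Two stronger readings are tempting. A reader might infer that the percentages largely rank devices by how common they are. The protocol gives no use rates, and the assumed ranges point both ways, so this is not supported. A reader might also infer that all respondents are the only available denominator. The form first asks whether the respondent has had work-related symptoms, so those answering yes are another, although that choice does not separate users from non-users either.

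**Conclusion.** The gap holds on the text alone: the item has no option for non-use or none, no preliminary item records use, and the post-surgery items do not supply it. Its percentages cannot separate how common a device is from how often it elicits symptoms among users.

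The size is unknown. It rests on use and symptom rates that the protocol does not give, and under the assumed ranges it runs from dominant (rank correlation 0.91 with use, 0.18 with symptom rate) to small (0.15 and 0.93). Misordering is possible, not established.

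The point is minor. It concerns one descriptive baseline item and does not touch the primary outcome or the linear mixed model. The difference in device names between forms is a separate small inconsistency that can be mended at the same time.

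**What to change.** Before the preliminary form is given out:

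- Keep the comparative wording of the item, but give each device its own row with three choices: do not use; use, symptoms not more frequent; use, symptoms more frequent. An empty row then means only that the question was not answered.
- For each device, report the count with more frequent symptoms over its users, with an exact interval, beside the share of all respondents.
- Use one set of device names on the preliminary form and both post-surgery forms, settling whether endoscopic instruments, laparoscopic equipment or both are meant.

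The cost is one reworked item, one aligned label and a few more ticks per respondent. Intervals for rarely used devices will be wide, and the report should say so and not rank them.
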